### **9.3. Vital Signs**

Descriptive summaries of actual values and changes from baseline will be calculated for systolic blood pressure, diastolic blood pressure, pulse rate, respiratory rate, oral body temperature, body weight, height and BMI. Height will be presented at baseline only.

### **9.4. Physical Examinations**

Abbreviated physical examinations will be summarized using descriptive statistics at Baseline and at each post-baseline time point. Shifts from Baseline will also be summarized.

Abnormal physical examination findings will be displayed in a by-subject listing.

### **9.5. Electrocardiograms**

Descriptive summaries will be presented for ECG measures of PR interval, RR interval, QRS Duration interval, QTcF interval, and HR. These summaries will be presented by study visit.

Shift tables comparing baseline ECG investigator interpretation (normal; abnormal, not clinically significant; or abnormal, clinically significant) and unable to evaluate, to each study visit will be provided.

### **9.6. Prior and Concomitant Medication**

Prior and concomitant medication use will be summarized descriptively using counts and percentages by ATC Class Level 2 and preferred term (ATC Class Level 5).

Prior medications will be presented separately from concomitant medications. Medications that started prior to Day 1 will be considered prior medications whether or not they were stopped prior to Day 1. Any medications continuing or starting after Day 1 will be considered to be concomitant. If a medication starts prior to Day 1 and continues after Day 1 it will be considered both prior and concomitant.

- Medications will be coded using the World Health Organization Drug Dictionary Version March 2021.

Medications will be summarized separately for non-corticosteroid medications and other corticosteroid (i.e. not Prednisone/Prednisolone) medications.

### **9.7. Long Term Extension Analysis**

The Long Term Extension endpoints will be summarized descriptively. Summaries of patient disposition, demographics, and baseline characteristics will be provided. The number of received doses and treatment duration will be described. Safety data including adverse events, laboratory evaluations and vital signs assessments will also be summarized. Specifically,

- Nature, frequency, and severity of adverse events, including serious adverse events, adverse events leading to discontinuation and possible corticosteroid-related adverse effects during the LTE from Week 61 to Week 113, will be summarized descriptively

- in a manner similar to that described in Section 9.1.
- Average daily dose of CS from Week 61 to Week 113 will be summarized by treatment group in double-blinded portion and overall.
  - Time to relapse from Week 61 (beginning of LTE) during the LTE will be summarized using Kaplan Meier estimates of the median and other quartiles along with two-sided 95% confidence intervals. The number of events and censored observations will be presented as well as graphical representations of estimated survival curves.

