#### **Long Term Extension Endpoints**

- Nature, frequency, and severity of adverse events, including serious adverse events, adverse events leading to discontinuation and possible corticosteroid-related adverse effects during the LTE from Week 61 to Week 113
- Average daily dose of CS from Week 61 to Week 113
- Time to initial relapse/flare from initial CDA to Week 109.

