### **9.3.9 Long term extension analysis**

The long term extension endpoints will be summarized descriptively in general. Summaries of patient disposition, demographics, and baseline characteristics will be provided. Safety data including AEs, laboratory evaluations and vital signs assessments will also be summarized. More details will be provided in the SAP.

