### 2.3.5. Long Term Extension Endpoints

- Nature, frequency, and severity of adverse events, including serious adverse events, adverse events leading to discontinuation and possible corticosteroid-related adverse effects during the LTE from Week 61 to Week 113
- Average daily dose of CS from Week 61 to Week 113

- Time to initial flare/relapse from initial CDA to Week 109.

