Relapse/flare can only happen following an initial CDA, subjects never achieve CDA prior to Week 37 will not be included in analysis. After the first initial flare, a patient can have additional relapse/flare, but only after the patient returns to CDA first, and then the next relapse/flare can happen. A similar method will be used to identify the number of relapses/flare from Week 37 to Week 61.

- Time to initial flare/relapse after initial CDA: Outcomes and durations for specific cases will be based on [Table 5](#). The date of the event/censoring is considered the end date and the date of initial CDA is considered the start date, for duration calculations.

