**Table 5: Event and Censoring Details for Time to First flare/relapse after initial CDA**

Situation	Date of First flare/relapse or Date of Censoring	Censored/ Event
No assessments after first CDA	Date of first CDA	Censored
Flare/relapse before Week 37	Date of first relapse	Event

Situation	Date of First flare/relapse or Date of Censoring	Censored/Event
Rituximab administered	Date of first Rituximab administration	Censored
No flare/relapse during the Blinded Treatment Period	Date of last efficacy assessment during blinded treatment phase (through Week 37)	Censored
Study discontinuation	Date of last efficacy assessment prior to or on the date of treatment discontinuation	Censored
Death before flare/relapse	Date of death	Censored

- Note: Patients will be censored prior to a flare/relapse event should a censoring reason occur. Censoring reasons may be categorized for reporting (e.g. by discontinuation reason). A patient must have a CDA in order to be included in this analysis.
- Complete remission for  $\geq 8$  weeks on zero CS at Week 61 = Yes if complete remission status is achieved at Weeks 53, 57, and 61 with no recorded CS usage during this time; No otherwise, provided all data is complete for the specified visits. For patients with missing data at the specified visits this endpoint value will be missing unless there are a documented CR both before and after the missing visit.
- TEAE = any adverse event with an onset date on or after the first dose of study drug, having been absent pre-treatment or worsening relative to pre-treatment state.
- TEAE (Blinded Treatment Period) = any TEAE with an onset date on or after the first dose of study drug and occurring before enrollment into the open-label portion of the study. TEAEs that are ongoing at the time of enrollment into the open-label portion are considered part of the double-blind portion of the study.
- TEAE (Open-Label Extension Period) = any TEAE with an onset date on or after enrollment into the open-label extension portion of the study, having been absent during the double-blind portion or worsening relative to double-blind portion state. Since the TEAE time is not collected for the study, any AE started or worsened on the first day of the open-label period is considered a TEAE for the blinded treatment period.

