	Cumulative duration of CR with a CS dose = 0 mg/day (days) from Baseline to Week 61	Zero-inflated negative binomial with terms for treatment group and disease history with an offset term based on the number of days on study during the Open-Label Extension Period
	GTI scores at Week 37	Analysis of covariance, with treatment, disease history as fixed effects, and baseline GTI score, baseline CS dose as covariates
	Change from Baseline in PDAI Score at Weeks 5, 13, 25, 37, and 61	MMRM with terms for treatment, week, baseline score, disease history, and treatment by week interaction
	Change from Baseline in ABQOL Score at Weeks 5, 13, 25, 37, and 61	MMRM with terms for treatment, week, baseline score, disease history, and treatment by week interaction
	Proportion of patients with ABQOL Score of zero at Weeks 5, 13, 25, 37, and 61	Cochran-Mantel-Haenszel test stratified by disease history at each visit
	Change from Baseline in EQ-5D-5L visual analog scale [VAS] results and individual dimension score categories at Weeks 5, 13, 25, 37 and 61	Continuous outcomes: MMRM with terms for treatment, week, baseline score, disease history, and treatment by week interaction. Categorical outcomes: Cochran-Mantel-Haenszel test stratified by disease history

	Endpoint	Analysis Method
	Time to first flare/relapse from initial CDA to Week 37	Log rank test stratified by disease history
	Time to first CR with a CS dose $\leq$ 10mg/day, from Baseline to Week 61	Log rank test stratified by disease history
	Proportion of patients with 3 or more lesions within 1 month or extension of established lesions that do not heal spontaneously within 1 week from Baseline to Week 37	Cochran-Mantel-Haenszel test stratified by disease history
	Total number of disease flares/relapses from initial CDA to Week 37	Zero-inflated negative binomial with terms for treatment group and disease history with an offset term based on the number of days on Post initial CDA

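### SAP 9.7 starts the LTE relapse clock at Week 61, and no analysis is specified for the endpoint as defined, from initial CDA to Week 109

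*SAP*

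**What the plan says.** SAP 2.3.5 lists three LTE endpoints. The one on relapse is "Time to initial flare/relapse from initial CDA to Week 109". The protocol has the same endpoint, in the synopsis and in Table 5 of section 3: "Time to initial relapse/flare from initial CDA to Week 109".

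On analysis, protocol 9.3.9 says "The long term extension endpoints will be summarized descriptively in general" and leaves the detail to the SAP. SAP 9.7 opens with "The Long Term Extension endpoints will be summarized descriptively" and then names three specific summaries. The relapse item reads "Time to relapse from Week 61 (beginning of LTE) during the LTE will be summarized using Kaplan Meier estimates".

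A CDA-anchored clock does exist elsewhere in the SAP. Section 6.1.8 states that "the date of initial CDA is considered the start date, for duration calculations". Table 5 then censors a flare-free patient at "Date of last efficacy assessment during blinded treatment phase (through Week 37", so no later than the end of the blinded period. The matching row of Table 6 is "Time to first flare/relapse from initial CDA to Week 37". SAP section 10, on changes from the planned analysis, is marked not applicable.

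**The concern.** The endpoint asks how long a patient stays free of a first flare once disease control is reached. The analysis in 9.7 asks how long a patient who has entered the LTE goes without a relapse from that entry. These are different questions in different patients.

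Protocol 1.1 makes the SAP the final authority for statistical analyses, so a programmer working from 9.7 would produce only the Week 61 curve. This is the only relapse measure among the three LTE endpoints, and long-term efficacy is part of the LTE objective. What is at stake is whether the final report contains the endpoint that it lists, and whether the Week 61 curve could be taken for it.

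**Working it through.** The plan attaches no event count, power or alpha to this endpoint, so there is no stated figure to reproduce. The check compares the definitions and then measures the two time axes.

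**Definitions side by side**

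| Element | Endpoint (SAP 2.3.5; protocol synopsis and Table 5) | Analysis (SAP 9.7) |
|---|---|---|
| Origin | Initial CDA | Week 61 |
| Event | First flare or relapse | A relapse during the LTE, not necessarily the first |
| Risk set | All patients who reach CDA | LTE entrants |
| Horizon | Week 109 | End of LTE |

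**Search for a CDA-to-Week-109 analysis elsewhere in the SAP**

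- 6.1.5.2: the rituximab censoring rule for time to flare names only the Week 37 endpoint.
- 6.1.8 and Table 5: origin at CDA, but censoring through Week 37.
- Table 6: the CDA-anchored row stops at Week 37.
- 8.3: Kaplan-Meier, Cox and log-rank analyses from CDA, to Week 37.
- 8.4: flares from Week 37 to Week 61 and relapse after complete remission through Week 61, as counts or proportions rather than time from CDA.

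None supplies a derivation, censoring rule or Kaplan-Meier analysis from CDA to Week 109.

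**Risk set and event.** Protocol 4.1 requires LTE entrants to have reached or held the end of the consolidation phase on low-dose corticosteroid between Weeks 37 and 61. It excludes those with more than one relapse above a stated corticosteroid dose, so one such relapse does not bar entry. A patient who first flared at, say, Week 20 can enter, starts the Week 61 curve without an event, and contributes a later relapse if one occurs.

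**Time axes.** Target days from SAP Tables 2 and 3: Week 3 = 15, Week 5 = 29, Week 37 = 253, Week 61 = 421, Week 109 = 757. The timing of CDA is an assumption.

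- Week 61 clock: 757 − 421 = 336 days (48 weeks).
- Defined clock: 757 − day of CDA.
- Share left out: (421 − day of CDA) / (757 − day of CDA).

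| CDA at | Defined clock | Left out by the Week 61 clock |
|---|---|---|
| Week 3 | 757 − 15 = 742 days (106 weeks) | 406 / 742 = 55% |
| Week 5 | 757 − 29 = 728 days (104 weeks) | 392 / 728 = 54% |
| Week 37 | 757 − 253 = 504 days (72 weeks) | 168 / 504 = 33% |

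A CDA later than Week 37 would lower the share further.

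**The case against.** The strongest reply is that little is lost. The opening sentence of 9.7 nominally covers every LTE endpoint, and the stretch from CDA to Week 37 is fully analysed in 8.3. Earlier flares appear elsewhere too: number of flares and proportion with at least one flare to Week 37 (8.3), flares from Week 37 to Week 61 and relapse after remission (8.4). SAP 9.7 also labels its curve honestly, as starting at Week 61.

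This stands, and it rules out three stronger readings that a reader might infer:

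- That the endpoint is never estimated in any part. The segment to Week 37 is. What is missing is any specified analysis through Week 109.
- That the whole 36-week blinded period is lost. Only follow-up after CDA belongs to the endpoint: 253 − 15 = 238 days (34 weeks) for CDA at Week 3, and 253 − 57 = 196 days (28 weeks) for CDA at Week 9. Flares in that time are missing from this one curve, not from the SAP.
- That the SAP overstates durability. That would follow only if the Week 61 curve were reported under the endpoint's name, which the SAP does not do.

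It can also be said that a CDA-to-Week-109 curve has faults of its own. Placebo patients receive active drug from Week 37, so their curve mixes two treatments. Censoring patients who do not enter the LTE may be informative, because entry depends on response and relapse history. Both are true and need stating with the analysis, but neither makes the Week 61 curve an estimate of the defined endpoint.

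A lag between document versions does not explain the mismatch. The protocol's amendment history shows the CDA-anchored endpoint in Amendment 06, the version that the SAP cites, and SAP 2.3.5 already carries it.

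**Conclusion.** The inconsistency is real. The defined endpoint and the specified LTE analysis differ in origin, event and risk set, and no rule or Kaplan-Meier analysis takes the CDA-anchored clock past Week 37. Completers' follow-up in the specified curve is 336 days, against 504 to 742 days under the definition, so 33% to 55% of post-CDA time is left out of it. These figures rest on target visit days and on an assumed CDA between Week 37 and Week 3. They measure the time axis, not bias in an estimated relapse rate, which the documents give no data to calculate.

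Severity is minor. The endpoint is descriptive, is not in the hierarchy of SAP 6.1.4, and is due only at the third analysis, after the LTE (SAP 4.3). Type I error, power, and the primary and key secondary conclusions are unaffected.

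**What to change.** Either route resolves it.

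1. Add to SAP 9.7 a descriptive Kaplan-Meier analysis of time from initial CDA to first flare through Week 109, in all patients who reach CDA, by original arm and overall.
   - Extend Table 5 and the rituximab censoring rule in 6.1.5.2 past Week 37, covering discontinuation and non-entry to the LTE.
   - State that placebo patients switch to active drug at Week 37 and that censoring of non-entrants may be informative.
   - Keep the Week 61 curve, labelled as a summary of LTE entrants.
2. Or amend the endpoint in SAP 2.3.5, the protocol synopsis and protocol Table 5 to match 9.7, and declare the change in SAP section 10.

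The first route costs a paragraph of SAP text, new event and censoring rules after Week 37, and one further descriptive analysis. The second costs wording only, but needs a protocol change and gives up the CDA-anchored view beyond Week 37. Neither needs new data collection: the schedules of assessments already include the efficacy outcome assessment at every scheduled visit in the extension periods.

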## 10. Changes from Planned Analysis

Not applicable.

## 11. Other Planned Analysis

### 11.1. Pharmacokinetic and Pharmacodynamic Analysis

Individual and group PK (PRN1008 and metabolites as applicable) and PD (anti-desmoglein-1 and -3) data will be summarized, displayed graphically, and by descriptive statistics for each visit, where measured. Additional analyses may be described and reported separately.

### 11.2. Questionnaires and health economic Analysis

Analyses of the following two exploratory endpoints will be performed outside of CSR under the responsibility of the Health Economics Outcomes Research (HEOR) department of Sanofi.

- Number and type of hospitalizations, outpatient medical visits, concomitant medication use, adverse events and other relevant outcomes
- Change from baseline in PDAI by visit and the temporal relationship to changes in quality of life and health economic variables

